- Diagnostic referral to assess focal physical symptoms and / or signs that were either a chief complaint of the subject or were elicited by the healthcare practitioner (excluding focal breast pain in the absence of other positive clinical findings).
- Interval Clinical Problems (symptoms or physical findings excluding isolated focal breast pain, that have developed between yearly mammograms).
- Other referrals to diagnostic conventional ultrasound including subjects younger than 30 years old for a clinically suspicious area, or subjects referred from a screening MRI because of an

abnormality.

These subpopulations will be analyzed in aggregate as well as individually.

The Imagio diagnostic ultrasound component will serve as the "internal control".

The specificity determined by a 2% POM is the primary effectiveness endpoint while the sensitivity is the secondary effectiveness endpoint.

Multiple effectiveness endpoints will be assessed (one primary and four secondary) so the overall 5% Type I error will be controlled by requiring two-sided p=0.01 to establish statistical significance. Specificity will be tested first according to a superiority test while sensitivity will then be tested according to non-inferiority tests. Testing will be based on the specificity (primary endpoint) and sensitivity (secondary endpoint), both based on a 2% Probability of Malignancy (POM). The overall specificity exceeding 40% will also be tested. In addition, downgrading benign masses and upgrading malignant masses using Imagio relative to the site and relative to IUS will be evaluated.

The superiority test and the non-inferiority tests will each have at least 80% power to test their respective hypotheses according to a two-sided test with overall 1% Type I error. The histopathology findings of the biopsy procedure will serve as a gold standard for Imagio. The decision to not recommend a biopsy during the first 12 months together with a negative 12 month clinical and imaging follow-up and no evidence of a >20% increase in the mass will be regarded as evidence of no disease (True-Negative for a negative OA/FN for a positive screening OA) for those initially not recommended for biopsy.

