A total of 7 independent radiologists will be assigned per each case to independently evaluate both image sets (IUS and Imagio) per subject. In addition, 3 other independent readers will perform the reimbursement reads. All independent readers will evaluate all Pivotal Study cases; the readers will also review 5% of all cases to assess temporal trends and consistency; the initial evaluation will be used in all analyses.

Each registration reader will review the data from the two image sets (IUS, Imagio) for each case; each reader will evaluate Imagio according to a pre-determined diagnostic rule set based on OA image characteristics and will similarly evaluate IUS according to another pre-determined diagnostic rule set and each reader will estimate the probability that the mass is cancer on a scale from 0% to 100% in 5% increments (1% if \leq 10% or \geq 90%). Readers will assess IUS and Imagio in this pre-defined order during independent review sessions; this pre-defined order is consistent with medical practice.

Registration readers will also have access to the results of two locked nomograms to separately predict the POM and the probability of cancer. These nomograms were constructed from the Pilot Study cases using a linear model for the POM and a logistic regression model for the probability of cancer. The nomograms are constructed from the five feature scores for Imagio from a blinded review performed by [name]. The registration readers do not need to use the results of the nomograms in making their POM judgments, but they will immediately see the two predictions as soon as they score the five

features. The sensitivity and specificity of the nomograms will also be evaluated using the average predicted score; if the average is ≤ 0.1 , then the case is predicted to be benign.

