8.5. Analysis Definitions

The final data for diagnostic test sensitivity and specificity will be presented in terms of a 2×2 table as follows; the threshold for defining a positive POM will be 2% corresponding to clinical practice standards:

Table 5: 2 x 2 Table

	Cancer	Benign
Test +	True Positive (TP)	False Positive (FP)
Test -	False Negative (FN)	True Negative (TN)

The above 2x2 table will also be constructed separately for Imagio and the Imagio diagnostic ultrasound component relative to a cancer or benign diagnosis. In addition, these 2x2 tables will also be generated for immediate biopsies, for delayed biopsies, for all biopsies, and for all cases including those not biopsied; discordant pairs for sensitivity as well as specificity will be analyzed. Those subjects without a biopsy will be excluded if they were not followed without a subsequent clinical evaluation.

A subject will be assigned to a row in the table depending on the respective diagnostic test result. Subjects with a diagnosis (biopsy or 11 month follow-up with no biopsy) will be assigned a column in the table according to the following rules:

- 1. If the result of the biopsy results in a cancer diagnosis, then the subject will be assigned to the Cancer column.
- 2. If the result of the biopsy results in a benign diagnosis, then the subject will be assigned to the Benign column.
- 3. If the biopsy was not performed and the subject was evaluated after 11 months post-baseline (nominal 12 month evaluation), then the subject will be counted as TN as long as there were no contrary clinical or radiologic findings (not to be based on Imagio); any mass declared to have any contrary clinical or radiologic findings will be declared to be a False-Positive if the Imagio POM was ≤2%; otherwise the subject will not be included in the table
- 4. If the baseline Imagio evaluation was not performed or declared to not be useable, then the subject will not be included in the table.

In addition, the cancer group will be further divided into invasive carcinoma and DCIS categories and each of these two categories will be assessed separately within a 2x2 table.

The use of the terms *sensitivity* and *specificity* is justified in this study because the biopsy and 11 month evaluation (12 month nominal evaluation) is the gold standard. The following statistical endpoints will be assessed for each image set:

- The true positive rate (TPR) or sensitivity of the test is defined as TP/ (TP + FN)

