- The specificity of the test is defined as TN/ (TN + FP)
- The concordance of the test is defined as (TP + TN)/N
- The positive likelihood ratio is defined as TPR/FPR
- The negative likelihood ratio is defined as (1 TPR)/(1 FPR)
- The positive predictive value (PPV) is defined as TP/(TP + FP)
- The negative predictive value (NPV) is defined as TN/ (TN + FN)
- The *odds ratio* (OR) is defined as (TP/FP)/(FN/TN)

Given that biopsy decisions are made using the 2% POM, POM levels >2% have limited relevance to the 2% threshold now widely used for making biopsy decisions.

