8.7. Analyses

8.7.1 Sensitivity and Specificity

The specificity for Imagio relative to the Imagio ultrasound component (IUS) will be assessed using a one-sided 99.5% lower confidence bound. The goal is to establish at least a 6% absolute advantage in specificity for Imagio vs IUS.

Seno Clinical Study Protocol: PIONEER-01
300176 Rev 8 PIONEER 01 Protocol Amendment 3.2

The sensitivities and specificities will be displayed for Imagio relative to IUS; in these displays, the consequences of Imagio (positive vs. negative) will be considered and compared using a generalized linear model (GENMOD) to account for correlated outcomes among the readers.. Additional analyses will be performed using the nomograms for the POM and the diagnosis based on the five Imagio features. The first nomogram models the probability of malignancy (NPP) while the second nomogram models the probability of cancer (NPC). The sensitivity and specificity of the averaged prediction (NPP and NPC) being ≥ 0.1 or ≤ 0.1 will be evaluated. The ability of the nomogram to downgrade benign masses with IUS POM $\leq 30\%$ and CDU POM $\leq 30\%$ will also be assessed. The linear regression (NPP) and the logistic regression (NPC) models behind the predictions are based solely upon the Pilot Study data.

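### Nomogram sensitivity and specificity are evaluated only at 0.1, five times the protocol's 2% positive threshold, so they are not comparable with the reader results; the nomogram downgrade set also departs from Hypothesis 5

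*Protocol*

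**What the plan says.** Two nomograms were built from the Pilot Study feature scores, "using a linear model for the POM and a logistic regression model for the probability of cancer" (Section 8.1.1). Section 8.7.1 calls their outputs NPP and NPC. Section 8.1.1 gives the decision rule: "features. The sensitivity and specificity of the nomograms will also be evaluated using the average predicted score; if the average is ≤ 0.1", the mass is taken as benign. Section 8.7.1 restates it: "The sensitivity and specificity of the averaged prediction (NPP and NPC) being ≥ 0.1 or ≤ 0.1 will be evaluated".

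Everywhere else the operating point is 2%. Section 8.1.1: "The specificity determined by a 2% POM is the primary effectiveness endpoint". Section 8.5: "the threshold for defining a positive POM will be 2% corresponding to clinical practice standards". The same section closes with this remark: "Given that biopsy decisions are made using the 2% POM, POM levels >2% have limited relevance to the 2% threshold now widely used" for such decisions. Section 8.7.4 displays all accuracy measures at 2% POM.

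Section 8.7.1 adds a second nomogram analysis: "The ability of the nomogram to downgrade benign masses with IUS POM" of at most 30% and CDU POM of at most 30%. It does not say what nomogram result counts as a downgrade. Hypothesis 5 (Section 8.2.5) defines downgrading for the trial as a move from BI-RADS 3, 4a or 4b to BI-RADS 2 or 3. It places 4a at 2% to 10% and 4b at 11% to 50%.

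**The concern.** The same words, sensitivity and specificity, are used for two different operating points on the same scale. Section 8.7.1 describes NPP as a model of the probability of malignancy, which is the quantity that Section 8.5 cuts at 2%. A mass with NPP and NPC both at 0.08 is benign by the nomogram rule, yet positive under Section 8.5 and in the 4a range of Section 8.2.5. A cut at 0.1 labels almost the whole 4a range benign, although Section 8.2.5 ties the prevention of negative biopsies to a reduction to 1% or 2%.

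At stake is interpretation. A nomogram specificity at 0.1 will appear in the same section as reader specificities at 2%, and close to a 40% benchmark that also belongs to the 2% definition. It answers a different question from both. The downgrade analysis has a related weakness: its starting set is not that of Hypothesis 5, so the two downgrade rates would not describe the same masses.

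**Working it through.** The plan states no expected nomogram performance, so there is no figure to reproduce.

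**1. Ratio of cuts.** 0.1 (Sections 8.1.1, 8.7.1) divided by 0.02 (Section 8.5) = 5.

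**2. Direction, without assumptions.** For one fixed score, every mass at or below 0.02 is also at or below 0.1. Raising the benign cut can therefore only move masses from positive to benign. Specificity cannot fall and sensitivity cannot rise.

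**3. Size, under assumptions.** The document gives no coefficients, score distribution or AUC. Assume a calibrated equal-variance binormal score with an AUC of 0.80 to 0.95, and a cancer fraction p of 18% to 40% (the detection-rate range in Section 8.1.1). With d = √2 · Φ⁻¹(AUC) and t = logit(cut) − logit(p):

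- specificity = Φ((t + d²/2)/d)
- sensitivity = 1 − Φ((t − d²/2)/d)

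Example with p = 30% and AUC 0.90: d = 1.812 and d²/2 = 1.642.

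- Cut 0.02: t = −3.892 + 0.847 = −3.045, and specificity = Φ(−1.402/1.812) = 0.220.
- Cut 0.1: t = −2.197 + 0.847 = −1.350, and specificity = Φ(0.292/1.812) = 0.564.

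| Cancer fraction | AUC | Specificity, 0.02 | Specificity, 0.1 | Sensitivity, 0.02 | Sensitivity, 0.1 |
|---|---|---|---|---|---|
| 18% | 0.80 | 0.081 | 0.509 | 0.995 | 0.878 |
| 18% | 0.95 | 0.556 | 0.808 | 0.986 | 0.927 |
| 30% | 0.80 | 0.025 | 0.295 | 0.999 | 0.958 |
| 30% | 0.90 | 0.220 | 0.564 | 0.995 | 0.951 |
| 30% | 0.95 | 0.442 | 0.720 | 0.993 | 0.959 |
| 40% | 0.80 | 0.010 | 0.181 | 1.000 | 0.982 |
| 40% | 0.95 | 0.369 | 0.653 | 0.996 | 0.973 |

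Over the full grid the 0.1 cut adds 17 to 43 points of specificity and costs 2 to 12 points of sensitivity. In the 30%, AUC 0.90 row the same score lies below 40% specificity at one cut and above it at the other.

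**4. Averaging.** A linear model is not bounded at zero. A hypothetical pair NPP = −0.05 and NPC = 0.24 averages (−0.05 + 0.24)/2 = 0.095, which is benign. With NPP limited to 0–1, the average is (0 + 0.24)/2 = 0.12, which is positive. Nothing in the document shows that such a pair occurs. It shows only why the components should also be reported singly.

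**5. Downgrade set.** A ceiling of 30% cuts through 4b (11% to 50%), so a mass with IUS POM between 30% and 50% is in the Hypothesis 5 set but outside the nomogram set. With no lower limit, readings at BI-RADS 1 or 2 level may enter the nomogram set but are not in the Hypothesis 5 set.

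**6. Direction of the downgrade rate.** Suppose 30% of the set is already at 2% or below.

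- If the event is a nomogram value of at most 0.1, with assumed rates of 80% in those masses and 50% in the rest: 0.3 × 0.8 + 0.7 × 0.5 = 59%, against 50% without them.
- If the event is crossing from above 2% to 2% or below, with an assumed 30% of the rest crossing: 0.7 × 0.3 = 21%, against 30% without them.

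The sign depends on an event that the document does not define.

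**The case against.** The strongest reply is that nothing confirmatory depends on this. Section 8.7.1 presents the nomogram work as additional. None of Hypotheses 1 to 6 uses it, and it has no alpha and no success criterion. The cut is stated in advance, on models locked from Pilot data, and sensitivity is reported at the same cut as specificity. All of this stands, and it limits the point to comparability.

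It can also be said that Section 8.5 names only Imagio and its ultrasound component for its tables, and that an average of a linear and a logistic prediction is a composite index, not a POM. This carries less weight. NPP is described as a model of that same probability, the measures have the same names, and the protocol gives no other reason for 0.1.

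A third reply is that the details could sit in the statistical analysis plan. That is fair for the exact downgrade event. It does not cover the 0.1 cut or the 30% ceiling, both of which the protocol fixes itself. The apparent tie at exactly 0.1 in Section 8.7.1 is a wording slip, since Section 8.1.1 already assigns that value to benign.

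**Conclusion.** The point holds as a comparability defect in an additional analysis. The nomogram is evaluated only at a cut five times the trial's own threshold, against the protocol's own remark on levels above 2%, and without a reason. The direction of the difference is certain. Its size is not computable from the document, and the 17 to 43 points of specificity and 2 to 12 of sensitivity rest wholly on the assumed calibrated binormal score. Hypotheses 1 to 6 are untouched.

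Three stronger readings are tempting, and the document does not support them.

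- A reader might infer that the nomogram specificity is biased upward. It is a different point on the same ROC curve, fixed in advance and shown with its sensitivity. It misleads only if read against 2% results.
- A reader might infer that the nomogram downgrade rate is inflated. This follows only if a value of at most 0.1 is the downgrade event, which Section 8.7.1 does not say; under a crossing rule the missing lower limit reduces the rate.
- A reader might infer that the set needs a floor above 2%. Hypothesis 5 includes BI-RADS 3, with a benefit from 2% to below 2%, so such a floor would remove masses that the trial means to count.

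**What to change.** In Sections 8.1.1 and 8.7.1, report nomogram sensitivity and specificity at 2% beside the reader results: for NPC, for NPP limited to 0–1, and for their average. Keep 0.1 on the average as an exploratory operating point, labelled as not comparable with the 2% results, and count exactly 0.1 as benign as Section 8.1.1 already does.

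For the nomogram downgrade analysis, replace the 30% ceiling with the Hypothesis 5 starting set (IUS BI-RADS 3, 4a and 4b). Count a downgrade only when the nomogram prediction is below the IUS POM and lies in the BI-RADS 2 or 3 range (2% or less). Show BI-RADS 3 separately.

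The cost is a text change and a few extra table rows; the locked nomograms and the reads are untouched. The nomogram specificity at 2% will look less favourable than at 0.1. Any NPP value limited to zero will count as benign at 2%, so the NPP row alone is the least dependable, which is why NPC is shown separately.

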Imagio (diagnostic ultrasound plus opto-acoustics).

The final sample size of the Pivotal Study will be determined by an interim analysis after the first 800 Pivotal Study subjects (cases 101-900 passing Quality Assurance review) have been evaluated with Imagio plus the results of any pre-scheduled biopsies; the final sample size will depend on the numbers of masses biopsied, the percent of biopsied masses with a cancer diagnosis, and the sensitivities and specificities for Imagio and IUS among biopsied masses. The interim analysis will be conducted once at least four of the seven registration readers complete the review of the 800 cases. Results will be shared with partners for business planning purposes but will not be shared with sites or published until the study is completed.

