5.5 Truth Panel

The Truth Panel will consist of a histopathologist and at least two radiologists.

The histopathologist will review all pathology reports inclusive of core biopsy reports and surgical pathology reports for each subject with a biopsy for determining the definitive diagnosis and for identifying and resolving inconsistent information. Seno Medical representatives will provide the two reports to the histopathologist for review and adjudication. In addition, BMS and Seno Medical representatives will provide packets to the Truth Panel for selected cases as follows:

- Cases where the number or numbering of suspicious masses is under dispute (per IRs)
- Cases with questionable eligibility
- Cases with high risk histology's as identified by the Central Histopathologist
- Cases where individual IR's identified problems with specific image sets
- Cases not biopsied and being followed to determine if a mass was a True-Negative (TN)

BMS will provide selected images meeting the above criteria to the Truth Panel who will determine truth regarding benign or malignant for submitted imaging data.

The Truth Panel will collaborate to perform the following tasks:

- 1. Generate gueries to sites to be managed by Seno Medical
- 2. Complete a CRF per patient deeming truth regarding:
 - Number and location of specific lesions
 - Histologic opinion and interpretation including benign or malignant classification
 - Mass-specific True-Negative designation

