The Data Rights Document identifies the individuals who have rights and restrictions to the de-identified subject data. The investigator will not have access to the reader reviews (including the final interpretation). The independent readers will have access to relevant images used to make the decision to perform the diagnostic ultrasound in addition to the Imagio images in order to perform evaluations for the above-stated image series used to evaluate the subjects for the BI-RADs 4a or 4b classification and if a decision is made to biopsy. Seno will have access to reader results once the biopsy is completed and the image sets are read by all registration readers.

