Has at least one or up to three suspicious solid masses or suspicious complex mixed cystic and solid masses (as either the cause of the clinical or mammographic finding) that the investigator has characterized as either BI-RADS 4 or 5, a biopsy has been recommended for all masses and that subject has agreed to have a biopsy for each suspicious mass that has been identified.

Unbiopsied Group Criteria:

Has at least one solid mass, complex cystic and solid mass, or indeterminate cystic versus solid lesion (as either the cause of clinical or mammographic finding), that the investigator has characterized as BI-RADS 3 or has ≤2% POM, and for which the subject has chosen to have either biopsy or short interval follow-up. If greater than one mass is found and each mass is not recommended for biopsy, then only one mass of the site's choice will be designated as the primary mass and will be followed for up to 12 months; Ideally, the mass with the highest POM as per the investigator will be selected for follow-up.

6.2.3.Imaging Visit(s), Day 1 - 10

Within 10 business days of the completion of the Enrollment Visit and before any scheduled image-guided biopsy, the subject will undergo the Imagio study evaluation. The Imagio evaluation will be performed according to the Imagio Instructions for Use provided for this clinical study. Subjects may be asked to return to the clinic to repeat the Imagio scan if (a) the image quality is not acceptable for review by the independent evaluators and (b) they have not undergone a biopsy procedure. Seno Medical Instruments, Inc. or their designees may be present during the procedures to provide technical support.

The study data will be recorded using electronic data capture (EDC). Any adverse events that occur during this Visit will be entered into the eCRF.

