The final sample size of the Pivotal Study will be determined by an interim analysis after the first 800 Pivotal Study subjects (cases 101-900 passing Quality Assurance review) have been evaluated with Imagio plus the results of any pre-scheduled biopsies; the final sample size will depend on the numbers of masses biopsied, the percent of biopsied masses with a cancer diagnosis, and the sensitivities and specificities for Imagio and IUS among biopsied masses. The interim analysis will be conducted once at least four of the seven registration readers complete the review of the 800 cases. Results will be shared with partners for business planning purposes based on all 7 registration readers but will not be shared with sites or published until the study is completed. The final sample size will not exceed 2,400 masses.

The study design will require all images to be managed by an independent ICC according to FDA guidelines (FDA Clinical Performance Evaluation: Considerations for Computer-Assisted Detection Devices Applied to Radiology Images and Radiology Device Data – Pre-market Approval [PMA] and Pre-market Notification [510k] Submissions, October 21, 2009). The ICC will assign multiple readers per team to review all images leading to the decision to either perform a biopsy or to follow the subject for up to 12 months. To best replicate clinical relevance where mammography and conventional diagnostic ultrasound will be read first in practice, the image sets will be read in the following order:

- 1. Imagio diagnostic ultrasound alone
- 2. Imagio (diagnostic ultrasound plus opto-acoustics).

To preserve their independence and objectivity as well as to minimize bias, the independent readers must lock their IUS evaluations before being allowed to begin their Imagio evaluations; in addition, readers will NOT have access to any clinical data but will have access to biopsy outcomes once they record and lock their evaluations. Then readers will have controlled access to biopsy outcomes in units of 25 cases to simulate the real world setting where practicing radiologists receive outcomes.

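### The sponsor gets reader results case by case during the study while it selects central-pathology cases and helps supply Truth Panel packets, so truth status and exclusions can be settled knowing the index-test result

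*Protocol*

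**What the plan says.** **Flow of results.** The interim described in 3.1 and 8.1.1 sets the final size from, among other things, "the sensitivities and specificities for Imagio and IUS among biopsied masses". Section 3.1 then states: "Results will be shared with partners for business planning purposes but will not be shared with sites or published until the study is completed". Section 8.1.1 repeats this and adds that the released results rest on all seven registration readers: "Results will be shared with partners for business planning purposes based on all 7 registration readers but will not be shared with sites or published". Separately, 5.8 says: "Seno will have access to reader results once the biopsy is completed and the image sets are read by all registration readers". It attaches no condition of database lock or study end.

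**Sponsor's hand in the reference standard.** Sections 3.1, 3.3 and 5.7 let the sponsor's Medical Director choose which specimens go to central pathology. The criteria include lesions whose OA study is suspected to be falsely positive or falsely negative, some classic OA cases, and any other lesion the Medical Director designates. Section 5.7 says the central review is used for all analyses.

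**Sponsor's hand in adjudication.** Section 5.5 says: "BMS and Seno Medical representatives will provide packets to the Truth Panel for selected cases as follows". The list that follows includes disputed mass numbering, questionable eligibility, image problems raised by individual readers, and unbiopsied cases awaiting a true-negative decision. Section 8.3 names the first three of these as grounds for exclusion. Under 5.13 the Truth Panel has access to reader results.

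**Safeguards.** Section 8.6.1 provides no stopping rule, no decrease in sample size, and no use of the observed specificity difference in the re-estimation. Reads are locked before feedback (8.1.1), and the panel's radiologists are independent (3.3).

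**The concern.** In an accuracy study, truth status and case inclusion should be fixed by people who do not know the index-test result. Here the party that learns, case by case, how Imagio scored against biopsy also selects which diagnoses are re-read and helps supply the cases considered for exclusion. The panel that rules on them can see the reader scores too.

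H1 (specificity superiority) and H2 (sensitivity non-inferiority) both rest on those decisions. A positive result on either would be open to the criticism that truth and inclusion were settled with the answer in view. Keeping results from the sites does not meet this, because the discretion lies elsewhere.

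**Working it through.** The plan gives no figure for this point, so the main check sets the passages side by side.

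1. **Who knows.** Section 5.8 speaks of the biopsy in the singular and sets no end-of-study condition. Release case by case is the plain reading.

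2. **Who decides.** The Medical Director selects for central pathology (3.1, 3.3, 5.7). Sponsor representatives, with BMS, supply the panel packets (5.5). The panel decides, with reader results available to it (5.13).

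3. **What selection on the OA result does.** If a suspected false-positive or false-negative case is re-read and the diagnosis changes, that change can only turn an Imagio error into an Imagio success. For example, take a mass called benign that is Imagio-positive and IUS-negative. Reclassified as cancer, it leaves the specificity comparison as a pair against Imagio and enters the sensitivity comparison as a pair in its favour. Re-reading some classic OA cases works the other way, but no sampling fractions are given, so nothing makes the two balance. Selection could also rest on the Medical Director's own view of the OA images, so gating reader results under 5.8 alone would not close this route.

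4. **What the safeguards cover.** Section 8.6.1 restricts what enters the sample-size rule, not who sees results. Locked reads protect the readers' scores, not case selection. Independent panel radiologists help, but they are not blinded to reader results. By contrast, 6.2.3 does blind a sponsor-assigned sonographer to histopathology and reader scores; the same protection is not extended to those who handle packets or choose pathology cases.

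5. **Share of the trial.** The interim set is 800/1,700 = 47% of the minimum Pivotal size, or 800/2,400 = 33% of the cap (one mass per subject). Cases outside it number 1,700 − 800 = 900 to 2,400 − 800 = 1,600. Exposure also reaches back: the interim uses pre-scheduled biopsies, whereas unbiopsied masses receive their true-negative decision at about 12 months (6.2.5, 6.4). Truth status inside the 800 may therefore still be open.

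6. **How informative the interim could be (illustration, not a bias estimate).** Table 6 inputs are difference d = 6%, discordance η = 20%, one-sided 0.5% (z = 2.576) and 90% power (z = 1.282).
   - Plan's figure: n = (2.576√0.20 + 1.282√(0.20 − 0.0036))²/0.0036 = 822, or 839 with continuity correction. The plan states 860, within 3% of 839.
   - Assumption: 18% to 40% of the 800 are cancers (the detection-rate range in 8.1.1), leaving 656 to 480 benign masses.
   - Standard error = √(0.1964/n) = 1.7 to 2.0 points.
   - Chance of already passing the H1 threshold if the true difference is 6 points: Φ((0.06√n − 2.576√0.20)/√0.1964) = 81% to 64%.
   - These are high-side figures, since the interim accuracy concerns biopsied masses only, and they follow Table 6 in treating each mass as one pair.

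**The case against.** The strongest reply is that discretion is narrower than it looks. Most referral triggers in 5.5 are raised by others: the readers, or the central histopathologist. Only questionable eligibility has no named originator. The panel histopathologist reviews pathology reports for every biopsied subject, 3.3 has the panel adjudicate all cases, and the panel, not the sponsor, decides. Its access to reader results is given for safety alerts. Section 5.8 also mentions a Data Rights Document, not shown, that may restrict access.

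Much of this stands and limits the point. It does not reach the Medical Director's selection for central pathology, which is explicitly tied to the OA result and open-ended. Nor does it separate the panel's safety role from its truth role. An unseen document should not have to override protocol text.

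Several stronger readings are tempting but unsupported:
- **That release to partners itself biases H1.** Partners have no stated role in scanning, reading, pathology or truth.
- **That sponsor staff present at scans (6.2.3) can steer them.** Their role is technical support; trained clinicians scan, QA radiologists select images, and IUS and OA come from the same evaluation.
- **That the four-of-seven-reader trigger contradicts 5.8.** No passage says the sponsor runs or sees that analysis, and the released results use all seven readers.
- **That at least 900 cases are scanned or read after release.** Nothing pauses enrolment or reading at 800.
- **That the bias can be put in percentage points.** No count of affected masses is documented, and with results pooled over seven readers, one reader's discordance carries only about one-seventh of a mass.

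**Conclusion.** The point holds as a weakness in who knows the index-test result when truth and exclusions are settled. It rests mainly on 5.8 combined with 5.7, supported by 5.5, 8.3 and 5.13. The partner release in 3.1 and 8.1.1 is secondary: it adds circulation of comparative accuracy that the trial does not need for its stated interim purpose.

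The size of any bias cannot be derived from the document. What can be stated is that the interim set is 47% of the minimum Pivotal size, that some truth decisions within it may still be pending, and that its results could be highly informative about the primary comparison under the assumptions shown. Two readings are relied on: that access under 5.8 is case by case, and that the results released to partners include the Imagio and IUS accuracy that defines the interim.

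A reader might infer misconduct or formal type I error inflation. Neither is shown; the risk is operational bias.

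**What to change.** 1. **Section 5.8:** give the sponsor reader results only after truth status, eligibility and exclusions for all Pivotal masses are locked.
2. **Sections 3.1, 3.3 and 5.7:** select the central-pathology cases that feed the analyses by criteria that do not use the OA result, such as high-risk histology or discordance judged without OA. Keep OA-based selection for the separate exploratory histology correlation, after lock.
3. **Sections 5.5 and 5.13:** have truth and exclusion decisions made and recorded without reader probability-of-malignancy scores. Reader flags about image problems can still go forward without scores. Use reader results only for the existing safety-alert route through the Medical Monitor.
4. **Sections 3.1, 8.1.1 and 8.6.1:** return only the final number of masses from the interim, and defer release of comparative results to partners until study completion.

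The cost is protocol wording and access restrictions, with no additional subjects or reads. The downside is that partners and the sponsor wait for performance figures, and the OA-histology correlation work starts later.
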